### 5.1.1 Gender Distribution

No gender ratio has been stipulated in this study as the results of the preclinical and/or clinical studies did not indicate any difference in the effect of the study treatment in terms of efficacy and safety.

### 5.2 Inclusion Criteria

- Diagnosis of c-KIT and/or FLT3-ITD mutated t(8;21) AML i.e.
  - $\circ$  >20% myeloid blasts in bone marrow and/or peripheral blood at initial diagnosis
  - Plus cytogenetic diagnosis of aberration t(8;21)/AML1-ETO

- Plus mutation of c-KIT gene (mut-KIT17 or mut-KIT8) or FLT3-ITD mutation or both c-KIT and FLT3-ITD mutations
- Chemo-responsive disease\* as determined by early bone marrow assessment on day 14-16 after first cycle of standard induction therapy with seven-day continuous infusion of 100-200 mg/m^2 cytarabine per day in combination with three doses of daunorubicine, or idarubicine, or mitoxantrone
- Age 18 65 years
- Fit for intensive chemotherapy as assessed by
  - Adequate liver and renal function as assessed by the following laboratory requirements to be conducted within 7 days prior to screening:
    - Total bilirubin ≤ 1.5 times the upper limit of normal
    - ALT and AST ≤ 2.5 times upper limit of normal
    - Creatinine ≤ 1.5 times upper limit of normal
  - Adequate cardiac function, i.e. left ventricular ejection fraction (LVEF) of >= 50% as assessed by transthoracal twodimensional echocardiography ("M Mode") or MUGA scan
- ECOG performance status of 0-2
- Life expectancy of at least 12 weeks
- Subject's written informed consent has been obtained
- Legal capacity (see also exclusion criterion)

\* Chemo-responsive non-refractory disease is defined by reduction of blast count and/or cellularity on the early bone marrow assessment on day 14-16 of the first induction treatment and peripheral blast clearance, i.e. the absence of myeloid blasts in peripheral blood on day 14-16 of the first induction treatment.

## 5.3 Exclusion Criteria

None of the following criteria may be present at the time of registration/screening:

- Primary refractory or previously relapsed AML
- Therapy-related AML after prior radiotherapy or chemotherapy
- Non-eligibility for high-dose cytarabine based consolidation, e.g. intolerance to cytarabine
- Inability to swallow oral medications
- Symptomatic congestive heart failure as defined by left ventricular ejection fraction (LVEF) of ≤50% as assessed by transthoracal twodimensional echocardiography ("M Mode") or MUGA scan
- Subject without legal capacity who is unable to understand the nature, significance and consequences of the study
- Investigational drug therapy outside of this trial during or within 4 weeks of study entry

• Known or persistent abuse of medication, drugs or alcohol

### Women\*

- Current pregnancy, nursing period
- Failure to use one of the following safe methods of contraception:
  - o Female condoms, diaphragm or coil, each used in combination with spermicides
  - o Intra-uterine device
  - Hormonal contraception in combination with a mechanical method of contraception

### \* Participation of Women

Women can only take part in this study if the risk of becoming pregnant is absolutely minimised. Therefore, only the following conditions are suitable:

- Women who use safe contraception throughout the duration of the study (i.e. from the time of written consent until 4 weeks after the final administration of the study medication) and have a negative pregnancy test one week before study entry
- Surgically sterilised women (tubal ligation, hysterectomy) with a written certificate issued by the treating physician
- Postmenopausal women who have not had a menstrual period for at least 2 years

Women of childbearing potential must be informed during the informed consent procedure that they must not become pregnant during the study (i.e. from the time of written consent until 4 weeks after the final administration of the study medication).

## 6 Enrolment of Subjects in the Study

## 6.1 **Prerequisites for Enrolment**

If a subject appears to be eligible for the study, the investigator will inform the subject or his/her legal representative / authorised agent (for subjects without legal capacity) about the study and ask the subject or the legal representative / authorised agent (for subjects without legal capacity) for his/her written consent (see also section 16/Ethical and Legal Principles).

It is imperative that written consent is obtained prior to any study-specific procedures. The investigator will then record the details of these trial subjects on the lists provided:

• Enrollment log: A confidential log of the names of all trial subjects with the identification code\* assigned to each subject at the time of enrolment in the clinical trial. With this list, the identity of each subject can be revealed. The list must be kept confidential and must not leave the institution; it

must remain at the study centre and must not be copied or otherwise passed on. Monitors, auditors and representatives of authorities must be allowed to inspect the list on request. The following details will be entered:

\* Subject identification code: A consecutive number is required for entry in study documents. The acronym MIDOKIT identifies this particular study, the following 3 digits correspond to the number of the centre, the next 2 digits stand for the consecutively screened subjects at the particular centre, for example: MIDOKIT-001-01 (Centre 1, Subject 1).

## 6.2 Mode of Registration

The subject identification code assigned for the study will be entered on the registration form ("Patientenmeldebogen") and the questions on inclusion and exclusion criteria on the form ("Checkliste Ein- und Ausschlusskriterien) will be answered. The fully completed form will then be faxed to the SAL central study office (SAL-Studienzentrale Dresden) for registration:

### [contact]

### Registration times: Monday to Friday from 8:00 to 16:00

The SAL central study office will review the subject's details on the registration fax. It will then confirm the subject's enrolment in the study by fax. After confirmation, the treatment can be initiated according to the protocol.

### 6.3 Removal of patients from study

All patients reaching a primary efficacy endpoint of the trial (event) will discontinue study treatment and will be followed up until 25 months after study entry. The following events will lead to discontinuation of study treatment:

- Primary refractory disease, defined as failure to achieve a CR/CRi five weeks after the beginning of the second induction therapy
- Hematological relapse from CR/CRi
- Death from any cause

A patient who withdraws is one who discontinues participation in a clinical study for any reason. Patients may be withdrawn from the trial for the following reasons:

- At their own request or at the request of their legally acceptable representative
- If, in the investigator's opinion, continuation in the study would be detrimental to the patient's well-being
- At the specific request of the sponsor

Patients must be withdrawn also for the following reasons:

- In case of unacceptable toxicity or progressive disease
- In case of substantial non-compliance with the requirements of the study
- Positive beta-HCG test consistent with pregnancy. Pregnancy will be reported along the same time lines as a serious adverse event
- Use of illicit drugs or other substances that may, in the opinion of the investigator, have a reasonable chance of contributing to toxicity or otherwise skewing results
- Development of an intercurrent illness or situation which would, in the judgment of the investigator, affect assessments of clinical status and study endpoints to a significant degree
- Development of a second cancer that requires treatment
- Patient is lost to follow-up
- Period of > 64 days between the start of the last consolidation cycle and beginning of maintenance treatment
- Interruption in study drug administration for a period longer than 28 consecutive days during maintenance treatment

Relevant visit data will be entered into the CRF, and any unused study medication will be accounted for and returned for all subjects entered into the trial even if for a brief period of time. Subjects who discontinue study treatment will have relevant information completed and recorded in the CRF and medical record. All subjects who discontinue because of adverse events or clinical laboratory abnormalities should be followed up until they recover or stabilize and the subsequent outcome recorded.

In case of premature withdrawal of any cause, all data documented up to the date of withdrawal will be entered into the study analysis.

## 7 Treatment Plan and Procedure

### 7.1 Dosage/Dosing Regimen, Drug Administration, and Remission Control

After response to the first cycle of induction treatment has been confirmed in the screening procedures and confirmation for study registration has been given by the SAL central study office, patients will receive one more cycle of induction treatment with MidoDA, followed by a total of three cycles of MidoHiDAC consolidation. Chemo-responsive non-refractory disease is defined by reduction of blast count and/or cellularity on the early bone marrow assessment on day 14-16 of the

first induction treatment and peripheral blast clearance, i.e. the absence of myeloid blasts in peripheral blood on day 14-16 of the first induction treatment. Proof of chemo-responsive, non-refractory disease is required for patient inclusion.

### Second cycle of induction: MidoDA

Second induction will commence earliest day 22 after start of the first induction. It is allowed to postpone the second induction course if the patient has an uncontrolled infection or transitory contraindications against chemotherapy. The second course of induction can be started once these problems have been resolved.

#### **MidoDA**

Cytarabine	100 mg/m  IV over 24 hrs	days 1-7
Daunorubicine	60 mg/m  IV over 1 hr	days 3-5
Midostaurin	50 mg/m  (2 capsules) p.o. twice daily	days 8-21

Midostaurin 50 mg (two 25 mg capsules) is given twice a day by mouth on days 8-21. Patients should take their doses at approximately the same time each day, and approximately 12 hours should elapse between the morning and evening doses. Each daily dose should be given with food and a glass of water (approx. 240 ml). Patients should be instructed to swallow capsules whole and not chew capsules. If vomiting occurs, no re-dosing is allowed before the next scheduled dose.

For **response assessment**, a bone marrow aspirate (or bone marrow biopsy) must be performed one week after recovery of ANC  $\geq$  1000/µL and platelets  $\geq$  100,000/µL to document a complete remission. Remission assessment must be performed latest 35 days after the beginning of second induction, even if ANC or platelets are below the described threshold.

If response assessment shows < 5% myeloid blasts, the patient has achieved a CR/CRi and will continue consolidation treatment according to this protocol.

If response assessment reveals  $\geq$  5% myeloid blasts, the patient will be classified as primary refractory disease and will discontinue study treatment. Patients who discontinue study treatment will be followed up until 25 months after study entry.

At each bone marrow aspiration, material should be obtained and sent to the central SAL laboratory in Dresden for MRD diagnostics (see section 7.4).

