	survival (OS), Relapse-free survival	(RFS), morphologic and molecular				
	CR rate, incidence of AEs/SAEs, MR	D kinetics				
TIMETABLE	Enrolment of first subject (FPFV)*:	1 May 2012				
	Enrolment of last subject:	30 April 2016				
	End of trial for last subject (LPLV)*:	31 May 2018				
	Closing of database	31 July 2018				
	Conclusion of statistical evaluation:	1 August 2018				
	Integrated final report:	30 September 2018				
	Treatment duration per subject: 16 months					
	Estimated duration of follow-up 9 months					
	Study duration per subject 25 months					
	Planned interim analysis: none					
	*Study begin/end is generally the first/last visit of the first/last subject					
SAMPLE SIZE	n = 18 patients					
	midostaurin 50 mg (two 25 mg capsu	ules) is given in combination with the				
	second of two induction cycles and	in combination with three cycles of				
	gh-dose cytarabine (HiDAC) consolidation chemotherapies and					
	maintenance treatment in patients w	vith c-kit or FLT3-ITD positive t(8;21)				
	part of the study	gn. The first cycle of induction is not				
	Second cycle of induction chemotherapy (7+3 scheme).					
	Cytarabine 100 mg/m  days 1-7					
	Daunorubicin 60 mg/m  days 3-5					
	Midostaurin 50 mg (2 capsules) twice	e daily days 8-21				
	Triple consolidation chemotherapy:					
	Cytarabine 3000 mg/m  twice daily d	ays 1, 3, 5				
	Midostaurin 50 mg (2 capsules) twice daily days 8-21					

	Maintenance treatment:				
	Midostaurin 50 mg (2 capsules) twice daily continuously for 12 months				
Main Inclusion Criteria	
 
Diagnosis of c-KIT mutated t(8;21) AML i.e.
 
>20% myeloid blasts in bone marrow and/or peripheral blood at initial diagnosis
 
Plus cytogenetic diagnosis of aberration t(8;21)/AML1-ETO
 
Plus mutation of c-KIT gene (mut-KIT17 or mut-KIT8) or FLT3-ITD mutation or both c-KIT and FLT3-ITD mutations
 
Chemoresponsive disease as determined by early bone marrow assessment on day 14-16 after first cycle of induction therapy with cytarabine in combination with daunorubicine or idarubicine, or mitoxantrone
 
Fit for further intensive chemotherapy
 
Age 18-65 years
 
ECOG performance status of 0-2
 
Life expectancy of at least 12 weeks
 
[Exact list of inclusion criteria is specified in section 5.3]
 
				

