### 3.3 Choice of PKC412 Regimen

We have chosen to administer PKC412 at 50 mg bid as per the sequential regimen. The choice of the sequential regimen, rather than simultaneous regimen of PKC412 was based on the following considerations: In vitro data suggests that although additive and/or synergistic cytotoxic effects are observed when FLT3 inhibitors are given simultaneously, or after chemotherapy (chemo  $\Rightarrow$  PKC412), exposure of cells to FLT3 inhibitors before chemotherapy (PKC412  $\Rightarrow$  chemo) has antagonistic effects on cytotoxicity [24]. Thus the simultaneous regimen would translate into one mimicking an antagonistic interaction, particularly as relates to the effect of earlier doses (e.g. days 1-3) of PKC412 on later doses of cytarabine (e.g. days 4-7).

Recently, data have been published indicating a FLT3-ligand mediated reduction in efficacy of tyrosin-kinase inhibitors when given after chemotherapy instead of parallel to chemotherapy [25]. However, in study 2106, the tolerability of a combined regimen was low with patients mainly suffering from nausea and vomiting, leading to the selection of a sequential application of chemotherapy followed by midostaurin. Furthermore, the results by Sato et al. are derived from in-vitro models and have not been confirmed in a clinical setting yet. Finally, the findings on the influence of tyroskinkinase-receptor ligands on inhibitory efficacy seem to be specific for FLT3 while ligand levels seem to be independent from chemotherapy in the case of the KIT molecule ([name], personal communication). Since the incidence of c-KIT mutations in t(8;21) AML is much higher than the incidence of FLT3-ITD, the main number of patients will be diagnosed with c-KIT*mut* rather than FLT3-ITD. Considering all arguments, the investigators of this trial have decided to apply the sequential dosing schedule of midostaurin as used in study CALGB 10603/CTSU C10603 (RATIFY).

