The MIDOKIT study design also includes a continuous maintenance phase of single agent PKC412 at 50 mg bid for up to an additional 12 months. Standard therapy of adults with AML does not routinely involve a maintenance phase of chemotherapy after completion of consolidation. However, data in the literature [MRD w/FTL3] suggest that minimal residual disease that can be detected in AML patients with FLT3 mutation predicts rapid relapse once chemotherapy is completed. Thus the continued administration of an oral, non-cytotoxic and well-tolerated drug such as PKC412 post chemotherapy might continue to inhibit growth or even kill residual FLT3 mutated blasts present at the end of a routine course of chemotherapy to prolong survival has recently been demonstrated in newly diagnosed Ph+ALL patients. Patient survival is significantly improved compared to historical controls when the anti-bcr/abl drug Glivec/Gleevec is given to Ph+ALL patients throughout therapy, from induction to relapse, including a maintenance phase with Glivec alone post completion of chemotherapy [26].

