### **MidoHiDAC**

Cytarabine	3000 mg/m  IV over 3 hrs twice daily	days 1,3,5
Midostaurin	50 mg (2 capsules) p.o. twice daily	days 8-21

High-dose cytarabine (HiDAC) 3000 mg/m^2 will be given by intravenous infusion over 3 hours every 12 hours on days 1, 3, and 5. Serial neurologic evaluation will be performed before and following the infusion of high-dose cytarabine.

It is recommended to administer dexamethasone 0.1% or other corticosteroid ophthalmic solution 2 drops to each eye four times per day to begin 6-12 hours prior to the initiation of the cytarabine infusion and to continue for at least 24 hours after the last cytarbine dose.

Midostaurin 50 mg (two 25 mg capsules) is given twice a day by mouth on days 8-21. Midostaurin is not given from day 22 of the current cycle and day 7 of the next consolidation cycle. Patients should take their doses at approximately the same time each day, and approximately 12 hours should elapse between the morning and evening doses. Each daily dose should be given with food and a glass of water (approx. 240 ml). Patients should be instructed to swallow capsules whole and not chew capsules. If vomiting occurs, no re-dosing is allowed before the next scheduled dose.

For **remission assessment**, a bone marrow aspirate (or bone marrow biopsy) must be performed one week after recovery of ANC  $\geq$  1000/µL and platelets  $\geq$  100,000/µL to document a complete remission. Remission assessment must be performed latest 35 days after the beginning of each consolidation cycle, even if ANC or platelets are below the described threshold.

If remission assessment shows < 5% myeloid blasts, the patient has a sustained CR/CRi and will continue treatment according to this protocol.

If remission assessment reveals  $\geq$  5% myeloid blasts, the patient has a relapse from CR/CRi and will discontinue study treatment. Patients who discontinue study treatment will be followed up until 25 months after study entry.

At each bone marrow aspiration, material should be obtained and sent to the central SAL laboratory in Dresden for MRD diagnostics (see section 7.4).

Three cycles of MidoHiDAC shall be administered depending on adequate blood counts and sufficient organ function.

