### Midostaurin maintenance

Patients who continue in complete remission (by bone marrow aspiration and blood evaluation) after three cycles of consolidation therapy will receive midostaurin maintenance therapy. If, in the opinion of the investigator, the clinical condition of a patient does not allow a third cycle of MidoHiDAC, the SAL central study office should be contacted for medical advise. If the LKP agrees that the risk of serious adverse events is too high in case of a third MidoHiDAC application, midostaurin maintenance may commence after two cycles of MidoHiDAC.

Prior to initiation of midostaurin maintenance therapy, all significant acute toxicity from consolidation therapy must have resolved to grade 2. Maintenance will begin after hematologic recovery (ANC  $\geq$  1000/ µL, platelet count  $\geq$ 50,000/µL) from remission consolidation and no sooner than 14 days after the last midostaurin application in the last cycle of MidoHiDAC, i.e. earliest on day 36 after the beginning of the last cycle of MidoHiDAC. Maintenance treatment must be started before day 64 after the beginning of the last cycle of MidoHiDAC, i.e. patients who cannot start maintenance treatment until 64 days after the beginning of the last cycle of MidoHiDAC, i.e. patients who cannot start maintenance treatment until 64 days after the beginning of the last cycle of MidoHiDAC, i.e. patients who cannot start maintenance treatment until 64 days after the beginning of the last cycle of the last cycle of MidoHiDAC will stop study treatment and will be followed up until 25 months after study entry.

Maintenance treatment consists of continuous midostaurin application for 12 cycles with 28 days per cycle:

Midostaurin50 mg (2 capsules) p.o. twice dailydays 1-28Start of new maintenance cycle on day 29

Midostaurin 50 mg (two 25 mg capsules) is given twice a day by mouth on days 1-28. Patients should take their doses at approximately the same time each day, and approximately 12 hours should elapse between the morning and evening doses. Each daily dose should be given with food and a glass of water (approx. 240 ml). Patients should be instructed to swallow capsules whole and not chew capsules. If vomiting occurs, no re-dosing is allowed before the next scheduled dose.

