## 8 Investigational medicinal product: Midostaurin (PKC 412)

## 8.1 Description of the Investigational medicinal product

The study drug provided is midostaurin 25 mg. The study drug will be supplied by Novartis as soft gelatine capsules, packaged in child-resistant blisters. See Investigator's Brochure for further characteristics, mechanism of action, preclinical activity, side-effects, pharmacokinetics and Phase I studies and results of clinical trials.

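### The MidoDA dosing table gives midostaurin per square metre, against the capsule count in its own row and the flat 50 mg dose everywhere else

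*Protocol*

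**What the plan says.** Section 7.1, under the heading MidoDA, sets out the second induction cycle in a three-row table. Cytarabine and daunorubicin are dosed per square metre. The third row gives midostaurin as "50 mg/m 2 (2 capsules) p.o. twice daily" on days 8 to 21. The first sentence under the table reads: "Midostaurin 50 mg (two 25 mg capsules) is given twice a day by mouth on days 8-21".

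The other statements of the trial dose are all flat:

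- Synopsis: "Midostaurin 50 mg (2 capsules) twice" daily, for the same second induction cycle.
- Section 3.3, chemotherapy phase: "We have chosen to administer PKC412 at 50 mg bid as per the sequential regimen".
- Section 3.3, maintenance: "a continuous maintenance phase of single agent PKC412 at 50 mg bid".
- Section 7.1, MidoHiDAC table: "50 mg (2 capsules) p.o. twice daily".
- Section 7.1, Midostaurin maintenance: "Midostaurin 50 mg (two 25 mg capsules) is given twice a day by mouth on days 1-28".
- Sections 7.2.1.2 and 7.2.1.4, QTc rules: the reduced dose is 50 mg once daily, with no reference to body surface area.

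On capsule strength, section 8.1 says: "The study drug provided is midostaurin 25 mg".

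**The concern.** A dose per square metre and a fixed number of capsules cannot both hold across adult patients. The conflict sits in the operative dosing table for the investigational drug, in a trial planned for 25 centres (section 4.4).

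Two other parts of the protocol would not stop a misreading:

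- Section 7.2.3 says that all dosing follows body surface area from actual weight, and it does not exempt midostaurin.
- The supply rule would not block a doubled dose. Section 8.3.1 allows a patient two kits at a time, and section 8.2 puts 64 capsules in a kit.

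What is at stake is tolerability in one 14-day block. Section 2.2.2 reports that Study 2106 gave 100 mg twice daily with the same kind of chemotherapy, found it safe but poorly tolerated because of nausea and vomiting, and found tolerability acceptable after reducing to 50 mg twice daily. The daunorubicin interaction reported at 100 mg twice daily appeared only in the simultaneous arm, so it is not claimed for the sequential schedule used here.

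**Working it through.** **Inputs.** Capsule strength 25 mg (section 8.1). Two capsules per intake, two intakes per day (MidoDA row). Schedule: 14 days in MidoDA, 14 days in each of three MidoHiDAC cycles, and 12 maintenance cycles of 28 days (section 7.1). The protocol gives no body surface area, so 1.5 to 2.2 m² is assumed. It also gives no rounding rule for midostaurin, so rounding to the nearest whole capsule is assumed.

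**The protocol's own dose.** 2 capsules × 25 mg = 50 mg per intake, and 2 × 50 = 100 mg per day. This reproduces the flat dose given elsewhere.

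**The per-square-metre reading.** Dose per intake = 50 mg/m² × body surface area; capsules = dose / 25 mg.

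| Assumed area (m²) | Dose (mg) | Capsules, exact | Capsules, rounded | Given (mg) | Ratio to 50 mg |
|---|---|---|---|---|---|
| 1.0 | 50 | 2.0 | 2 | 50 | 1.0 |
| 1.5 | 75 | 3.0 | 3 | 75 | 1.5 |
| 1.6 | 80 | 3.2 | 3 | 75 | 1.5 |
| 1.8 | 90 | 3.6 | 4 | 100 | 2.0 |
| 2.0 | 100 | 4.0 | 4 | 100 | 2.0 |
| 2.2 | 110 | 4.4 | 4 | 100 | 2.0 |

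The two parts of the row agree exactly only at 1.0 m². With rounding, two capsules would be given only below 62.5 / 50 = 1.25 m².

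**Share of treatment affected.** Planned midostaurin days: 14 + 3 × 14 + 12 × 28 = 392. Only the MidoDA block carries the wrong unit: 14 / 392 = 3.6%.

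**Excess if misread.** Planned total: 392 × 100 mg = 39,200 mg. At 75 mg per intake the daily dose is 150 mg, so the excess is 14 × (150 − 100) = 700 mg, or 700 / 39,200 = 1.8%. At 100 mg per intake it is 14 × (200 − 100) = 1,400 mg, or 3.6%.

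**Supply check.** Two kits hold 2 × 64 = 128 capsules. The intended MidoDA block needs 2 × 2 × 14 = 56. Four capsules twice daily would need 4 × 2 × 14 = 112, so the doubled dose could be dispensed in full.

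**Is it a reading error from the PDF?** Unlikely. The unit is printed in full, and the matching MidoHiDAC row, which also sits below a chemotherapy row dosed per square metre, shows plain milligrams. A carry-over from the rows above is the probable source.

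**The case against.** The strongest reply is that the error is corrected where it occurs. The row itself states two capsules, the next sentence states the flat dose, and no part of the protocol gives a capsule count by body surface area. The QTc reduction to 50 mg once daily is a halving only if the starting dose is a flat 50 mg twice daily. A prescriber would have to override all of this to give more. The 1.5 to 2.0 range also depends on an assumed body surface area and an assumed rounding rule. If a misreading did happen, section 2.2.2 describes 100 mg twice daily as safe, though poorly tolerated, and the exposure would last 14 days. Section 7.2.3 concerns obese patients and closes by speaking of chemotherapy doses, so in context it does not govern midostaurin.

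Most of this stands. It shows that the intended dose is recoverable and that the practical risk is low, and it rules out rating the point above minor. It does not make the row correct: the unit still contradicts the rest of the protocol. Nor would a misreading be harmless, since section 8.4.2 says that midostaurin is somewhat less well tolerated with chemotherapy than alone.

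**Conclusion.** The row is wrong as written. The intended dose is a flat 50 mg twice daily, and on that best-supported reading the dose ratio is 1.0 and nothing changes for patients. If the printed unit were followed, intake would be 75 to 100 mg, which is 1.5 to 2.0 times the intended dose, over 3.6% of the planned midostaurin days. That range rests on the assumed body surface area and on whole-capsule rounding. The primary endpoint, sample size, decision rule and analysis are untouched. The point is minor, and the confidence in it is high.

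**What to change.** Delete the per-square-metre unit from the midostaurin row of the MidoDA table, so that it matches the corresponding row of the MidoHiDAC table, and notify the sites. As optional tidying, limit the body-surface-area rule in section 7.2.3 to cytarabine and daunorubicin.

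The cost is one unit deleted, a notice to sites, and whatever amendment step section 15.2 requires for a change to the protocol text. No statistical quantity has to be recalculated.
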